### ***Cumulative safety information***

OMT consists of exercises of tongue / lip muscle. There is no physical injury recorded but the therapy involves the use of time for training. Patients who will not master or have the effect of treatment may experience this as a burden.

### ***Cumulative efficacy information***

The concept of orofacial myofunctional disorders (OMD) refers to the abnormal resting posture of the orofacial musculature, atypical chewing, and swallowing patterns, dental malocclusions, mouth breathing, blocked nasal airways, and speech problems. This novel paradigm defines OSA as an OMD developing from early childhood. OMT aims to re-educate the movement of muscles, restore correct swallowing patterns, and establish adequate labial-lingual postures.

Recent systematic reviews of the effect of OMT on OSA conclude that OMT as a participatory health intervention is promising as mono therapy in mild to moderate disease, and as an adjunct to other therapies in moderate to severe disease. However, the need for further studies is also highlighted due to the small

number of studies available, heterogeneity of interventions and high risk of bias with low quality of evidence .

## **5.2 Time frame**

Data will be collected from August 2023 until August 2024.

## **6 Statistical analysis plan and power calculation**

OMTa adherence will be dichotomized by performance of  $\geq 85\%$  of exercises in three domains based on the electronic exercise diary. Patients non fulfilling these criteria will be classified as OMTa non-adherent. Results will be analysed as intention to treat regardless of OMTa adherence.

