## **Aims and hypotheses**

## **2.1 Overall research aims**

The overall aim of this study is to estimate the effect of OMT plus auto-monitoring (OMTa) compared to auto-monitoring alone. Moreover, we aim to identify anatomical and behavioural predictors of OMTa adherence.

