## **Participatory health technology**

The auto-monitoring application is named “Sleep Well”. The application communicates with a data cluster located in Iceland. The Sleep Well application contains a sleep diary. The diary is inspired by the consensus sleep diary developed by Carney and co-workers (appendix 1). Subjective, quantitative sleep data including sleep efficiency will be calculated based on the formulas proposed by Reed and co-workers. Exercises will be reported in an exercise diary in the sleep well application. A simple question for each of the three daily exercises will be delivered. Adherence to exercises will be assessed by the number of entries to the three daily questions. Administrative co-ordinators will support participants with technical issues.

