## **Outcomes**

The primary end point of the RCT is change in the AHI

Secondary endpoints:

1. Change in the Epworth Sleepiness scale and PROMs in the European Sleep Questionnaire.
2. OMTa adherence
3. Change in other conventional OSA severity indices (oxygen desaturation index, time below 90% saturation, nadir saturation) and change in novel OSA parameters in SAS identified in the development phase of the project.
4. Change in objective and subjective sleep quality (PSG and sleep diary, respectively).
5. Change in physiological parameters assessed by wearables.
6. Change in objective daytime functioning testing (PVT and Stroop test).
7. Change in self-reported self-efficacy as assessed by the PAM.
8. Changes in the Orofacial Myofunctional Evaluation with Scores (OMES).
9. Changes in the IOPI strength and endurance
10. Changes in hyoid position as assessed by a lateral cephalogram
11. Prediction of improvement in SDB severity by objective parameters from a 2D cephalogram obtained at baseline.

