### **6.1 Statistical analysis**

The Kruskal-Wallis test will be used for intergroup comparisons at each time point (T1 and T2). Intragroup comparisons will be performed by the Friedman test.

Inter-examiner agreement of OMT measurements will be determined by intraclass correlation coefficients (ICCs) and weighted kappa coefficient (Kw'). Effect sizes for statistically significant differences between T1 and T2 will be calculated using the Cohen's d statistic.

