### **6.2 Power calculation**

The number in each group is calculated to N=50 based on the results of Guimaraes et al. The AHI was used in the calculation.

Independent samples t-test, two-sided, anticipated effect size (Cohen's d) 0.8 (high), power  $\geq 80\%$ , probability level 5%. This gives a minimal sample size of 26 per group. The expected drop out of patients during the OMTa trial is 25% corresponding to a total of 20 patients. To accommodate for this potential dropout and to have adequate power for subpopulation analysis for gender, the sample size was increased to 100 (50 in each group).

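### OMTa adherence is defined for analysis only as a yes/no at 85%, although a graded diary count is collected and predictors of adherence are an overall aim resting on about 50 people

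*Combined protocol and SAP*

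**What the plan says.** Section 2.1 states a second overall aim beside the treatment effect: "Moreover, we aim to identify anatomical and behavioural predictors of OMTa adherence". The Outcomes section lists "OMTa adherence" as secondary endpoint 2.

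The Participatory health technology section describes the data: "Adherence to exercises will be assessed by the number of entries to the three daily questions". That is a graded count.

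Section 6 then says "OMTa adherence will be dichotomized by performance of" at least 85% of exercises in three domains, taken from the electronic exercise diary, and "Patients non fulfilling these criteria will be classified as OMTa non-adherent". It cites one earlier study for this and adds that results are analysed by intention to treat whatever the adherence.

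Section 6.1 names Kruskal-Wallis, Friedman, intraclass correlation, weighted kappa and Cohen's d. It assigns none of them to the predictor aim. Section 6.2 powers the AHI comparison only: "the sample size was increased to 100 (50 in each group").

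**The concern.** The graded measure exists, yet the only analysis variable in section 6 is the two-class one. On that variable a participant just under the cut counts the same as one who never exercised. The aim rests on one arm, because the waiting-list group does not have the treatment module during the 90 days.

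At about 50 people, information lost to a cut cannot easily be spared. A moderate predictor is more likely to be missed, and one that does reach significance is more likely to have an overstated effect. The plan also names no predictor list and no model for the aim, so both the form of the outcome and the choice of predictors could be settled after the data are seen.

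**Working it through.** **The plan's own figure.** Section 6.2 uses a two-sided 5% t-test, d = 0.8 and 80% power. The normal approximation gives 25 per group. The exact t calculation gives 25.5, so 26, with 80.7% power at 26. The stated 26 reproduces, but it concerns AHI. No power figure is given for the predictor aim.

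**Inputs from the documents.** The OMTa arm has 50 people (section 6.2). The cut is at 85% (section 6). A 25% dropout is expected (section 6.2), and 50 × 0.75 = 37.5, so about 37 if every dropout gives no diary data.

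**Assumptions, not in the documents.** The predictor and adherence are bivariate normal. Their correlation is r = 0.4, with 0.3 and 0.5 as a range. The share p reaching the cut is 50%, 25% or 15%; by symmetry 75% and 85% give the same results as 25% and 15%.

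**Loss from the cut.** Dichotomising multiplies the correlation by f = φ(z_p)/√(p(1−p)), where φ(z_p) is the normal density at the cut. Relative efficiency is f².

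| Share reaching the cut | f | f² | Information lost | Effective n of 50 |
|---|---|---|---|---|
| 50% | 0.798 | 0.637 | 36% | 32 |
| 25% or 75% | 0.734 | 0.539 | 46% | 27 |
| 15% or 85% | 0.653 | 0.426 | 57% | 21 |

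The median is the most favourable place for the cut, so 36% is the minimum loss on this scale.

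**Power.** By Fisher's z, power ≈ Φ(atanh(r)·√(n−3) − 1.96).
- Graded, r = 0.4, n = 50: atanh(0.4) = 0.424; 0.424 × √47 = 2.90; 2.90 − 1.96 = 0.94; power 83%.
- Cut at the median: r becomes 0.4 × 0.798 = 0.319; atanh = 0.331; 0.331 × √47 = 2.27; 2.27 − 1.96 = 0.31; power 62%.

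| n | r | Graded | 50% | 25% or 75% | 15% or 85% |
|---|---|---|---|---|---|
| 50 | 0.3 | 56% | 39% | 34% | 28% |
| 50 | 0.4 | 83% | 62% | 55% | 45% |
| 50 | 0.5 | 97% | 83% | 75% | 64% |
| 37 | 0.4 | 70% | 49% | 42% | 34% |

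Simulation at n = 50 and r = 0.4 agrees: about 83% for Pearson correlation on the graded measure, against 63%, 56% and 45% for a t-test between the two classes when 50%, 75% and 85% reach the cut. Spearman correlation gives about 79%, against 60%, 53% and 42% for Mann-Whitney.

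**Sensitivity to shape.** With bounded, skewed or U-shaped adherence (beta distributions cut at 85%, with 25% to 39% reaching it), n = 50 and r = 0.4, power was 79% to 82% graded against 57% to 62% dichotomised.

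**The case against.** The strongest reply is that section 6 defines a label and never says the predictor analysis will use it, while the app section describes a count. That stands. A reader might infer that the plan commits itself to a binary predictor analysis; the text supports only that the binary form is the one defined for analysis, so the loss is conditional.

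A reader might also infer that section 6.1 has no usable method. That goes too far: Kruskal-Wallis could compare a baseline measure between adherent and non-adherent participants. What is true is that the test is not assigned to this aim, handles one predictor at a time, and gives no adjustment for site or sex and no slope or interval.

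The power figures depend on a correlation, a distribution and adherent shares that the documents do not give. If adherence were truly two-class, the cut would cost less. The skewed and U-shaped cases tried still show a clear loss, but they do not cover that extreme.

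It is tempting to take about 37 as the working sample size. The documents do not say that people who drop out leave the adherence analysis. They may still have baseline measures and diary entries, and section 6 classes anyone not meeting the criterion as non-adherent. So 37 is a worst case.

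Nor do the documents give a ready percentage of prescribed exercises. The intervention section lists eight exercises (four tongue, two soft palate, two facial), most of them three times a day and one for 14 days only, whereas the app asks three questions a day. The measure that is clearly available is entries completed.

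Finally, the cut is pre-specified and cited, and prediction of adherence is not itself a listed endpoint. Both are true. They limit the weight of the point but do not remove an overall aim.

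**Conclusion.** The point holds in conditional form. The plan collects a graded adherence measure, defines only a binary one for analysis, and does not say which serves the predictor aim. If the binary one does, the loss is at least about 36% of the information when adherence varies smoothly, and less if it is nearly two-class. At n = 50 and an assumed correlation of 0.4 on a normal scale, power falls by about 21 to 38 percentage points (83 − 62 and 83 − 45), depending on the share reaching the cut.

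A reader might infer that the trial's main result is weakened. It is not: the AHI comparison is by intention to treat regardless of adherence. The change is worth making because it serves a stated aim at almost no cost.

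**What to change.** In section 6, state that for the predictor aim adherence is the proportion of expected diary entries completed over the intervention period: entries to the three daily questions divided by entries expected. Define the denominator. The protocol describes the intervention both as 90 days and as 12 weeks, which gives 3 × 90 = 270 or 3 × 84 = 252 expected entries; these statements must be reconciled. State also how entries map to the three domains behind the 85% class, and how participants who stop early are counted.

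Analyse this proportion in the OMTa arm by rank correlation, or by linear or fractional regression, adjusted for site and sex. Use a short, pre-named list of anatomical and behavioural baseline predictors and report estimates with 95% confidence intervals. The short list matters in its own right, because a graded outcome does not protect against chance findings among many candidates.

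Keep the 85% classification as a descriptive summary for comparison with the cited study.

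The cost is SAP wording, including the denominator, with no new data, visits or participants. The small downside is that the predictor results will be less directly comparable with work that uses a binary definition of adherence.

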## **3.0 Material and methods**

**The study is a single blinded RCT with blinded outcome evaluation and intention to treat analysis.** The participants will know by default if they are allocated to the OMTa or waiting list with auto-monitoring during the 90-day intervention period. Blinded baseline- and outcome assessments will be performed by one doctor ([name]) in Norway and one doctor ([name]) in Estonia.

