#### **After baseline evaluation:**

##### *Polysomnography (PSG)*

All patients, both intervention and waiting list group, will administer three nights of self-applied PSG (hereinafter called SAS). This is an alternative to in-lab services and PSG setups, in a self-applied form. The EEG is located only on the forehead (F-channels), with no electrodes located on the top of the scalp (C-channels) and back of the head (O-channels) as in traditional PSG. The self-applied setup facilitates

the use of multi-night studies to capture night-to-night variability and the participants apply the sensors themselves, using an instructional video provided by Nox. In this study, we will do three nights in a row twice. PSG will be performed before the baseline consultation and before the outcome evaluation. The equipment will be given out at baseline consultation. After use the patients will mail the equipment back to Ahus/FPH or bring the equipment back to the first treatment session.

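### Intention to treat is promised, but the tests named use only observed T2 values without baseline adjustment, and nothing is said about missing T2 data

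*Combined protocol and SAP*

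**What the plan says.** Section 3.0 describes the design: "The study is a single blinded RCT with blinded outcome evaluation and intention to treat analysis". Section 6 adds: "Results will be analysed as intention to treat regardless of OMTa adherence". Under Outcomes, "The primary end point of the RCT is change in the AHI", and the AHI comes from self-applied sleep recordings: "PSG will be performed before the baseline consultation and before the outcome evaluation".

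Section 6.1 names two tests for comparing arms and time points. Between arms: "The Kruskal-Wallis test will be used for intergroup comparisons at each time point (T1 and T2"). Within arm: "Intragroup comparisons will be performed by the Friedman test".

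Section 6.2 says: "The expected drop out of patients during the OMTa trial is 25% corresponding to a total of 20 patients". It answers this by enlarging the sample to 50 per group.

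No section defines the analysis set, a rule for missing T2 values, a model that uses baseline AHI, a missing-data sensitivity analysis, or whether participants who stop the exercises are still asked for the T2 recording.

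**The concern.** Kruskal-Wallis at T2 can use only participants who have a T2 AHI. Friedman needs both values from each participant and does not compare the arms. Neither test compares the change in AHI between arms, and neither uses baseline AHI to adjust for differences between those who remain. A larger sample replaces lost numbers but does not make those who remain comparable.

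Dropout could plausibly differ by arm. OMTa participants are asked for exercise sets three times a day for 12 weeks. The cumulative safety section accepts that people who do not master the exercises or do not benefit may find them a burden. Waiting-list participants have no exercises to abandon and are offered the programme only after the outcome evaluation. If those who leave OMTa are more severe, or respond less, the T2 comparison favours OMTa even when the treatment does nothing.

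**Working it through.** **1. The plan's own sample size (section 6.2).** Inputs: two-sided t-test, d = 0.8, power 80%, alpha 5%. The noncentral t calculation gives n = 25.5, so 26 per group (power 80.7%). The stated figure reproduces.

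**2. How many may lack T2.**
- 25% of 100 = 25, leaving 75 (37 or 38 per arm).
- The 20 patients stated are 20/100 = 20% of those randomised, leaving 80 (40 per arm). Twenty is 25% only of 80.
- If only OMTa loses 25%: 0.25 × 50 = 12.5, about 13 missing, leaving about 37 v 50.

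**3. Power.** Allowing for 25% dropout requires 26 / (1 − 0.25) = 34.7, so 35 per group; 50 are planned. At d = 0.8, 37 v 37 gives 92% power by t-test and about 91% by rank test. With two arms, Kruskal-Wallis is the Wilcoxon-Mann-Whitney test.

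**4. Dropout related to baseline AHI, no true effect.** The documents give no SD, correlation or dropout mechanism, so these are assumed: SD 6 events/h, T1-T2 correlation 0.6, 50 per arm, about 25% dropout in each arm. Dropout is random on the waiting list and depends on baseline AHI in OMTa. Simulated rejection rates at the nominal 5% level:

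| Odds ratio of OMTa dropout per SD of baseline AHI | Kruskal-Wallis at T2 |
|---|---|
| 1 (random) | 4.6% |
| about 1.65 | 5.8% |
| about 2.7 | 7.5% |
| about 4.5 | about 12% |

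With 4,000 trials, the 95% simulation error around 5% is 1.96 × √(0.05 × 0.95 / 4000) = 0.7 percentage points, so the 1.65 row is barely distinguishable from 5%. In the strongest case the spurious T2 difference is about −1.1 events/h. Adjusting for baseline AHI, even among completers only, brings the difference to about 0 and rejection to about 5%.

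**5. Dropout related to the T2 response.** Suppose the 25% who leave OMTa gain nothing and the others gain 0.8 SD. Completers show 0.8 × 6 = 4.8 events/h; all randomised show 0.75 × 4.8 = 3.6; the ratio is 1/0.75 = 1.33. The baseline-adjusted estimate among those observed stays at about −4.8, because baseline AHI carries no information on who failed to respond.

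Separately, take no true effect, 25% dropout in each arm, and OMTa dropout correlated 0.3, 0.5 or 0.7 with a poor outcome. The rank test then rejects in about 8%, 14% or 23% of trials, with a spurious benefit of 0.12, 0.20 or 0.28 SD.

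**The case against.** The strongest reply is that section 6 ties intention to treat to adherence and that Kruskal-Wallis at T2 honours this: a participant who skips the exercises but returns the T2 recording is analysed as randomised. That stands. A rank test also does not forbid imputation beforehand, and section 6.1 does not state that only observed data are used. The available-case result is what the tests give when nothing further is specified; it is not a declared completer set.

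The number affected is also uncertain. Section 6.2 does not say whether its dropout means stopping treatment or loss to follow-up, or whether it applies to both arms. An outcome session is scheduled for every participant and the recording is self-applied, so some who stop exercising may still supply T2 data.

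The two illustrations show different things. In step 4 the cause is the missing baseline adjustment rather than the exclusion of participants, since an adjusted analysis of completers removes the bias. In step 5 no baseline-adjusted model helps, and the overstatement by one third follows directly from the assumption.

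These replies limit the claim but leave the gap. The promise of intention to treat comes with no rule for participants without T2, and the named tests neither use baseline nor compare change between arms.

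**Conclusion.** The point holds in a limited form. As written, the primary comparison is an available-case rank test at T2 without baseline adjustment, in a trial that promises intention to treat and expects 20 to 25% dropout. False rejection of about 6% to 12% rests on the assumed SD of 6, correlation of 0.6 and baseline-related dropout in OMTa only. The upper end needs strong one-sided selection, and with random dropout the rate stays near 5%. Dropout related to response could do more harm, again under assumed correlations.

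A reader might infer four stronger things that the documents do not support:
- **That the analysis is per-protocol.** Non-adherers with T2 data are kept in their arm.
- **That a quarter of those randomised will certainly be lost.** The 25% and the 20 patients disagree for 100 randomised, and the share without T2 is not stated.
- **That the trial is underpowered.** For the overall comparison at d = 0.8 it is not.
- **That a mixed model alone would restore intention to treat.** With two time points, participants with only T1 add almost nothing about the treatment effect, and outcome-related dropout remains.

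**What to change.** 1. Define the primary analysis set as all randomised participants, in the arm assigned.
2. Name one primary analysis: the between-arm difference in T2 AHI adjusted for baseline AHI, site and sex, with a 95% CI. ANCOVA with multiple imputation, or an equivalent constrained longitudinal model of T1 and T2, would serve. Site and sex belong in it because the randomisation is separated by both. This handles dropout related to baseline and gains precision: at the assumed correlation of 0.6, residual variance falls to 1 − 0.6² = 0.64 of its unadjusted value. Keep the rank tests as supportive.
3. State that the already scheduled T2 recording is requested from participants who stop exercising.
4. Add a reference-based sensitivity analysis that imputes missing OMTa T2 values from the waiting-list arm. Under an assumed 13 of 50 OMTa dropouts with control-like outcomes, d falls from 0.80 to 0.8 × 37/50 = 0.59 and rank-test power is about 81%, so the trial can bear it.
5. Reconcile the 25% with the 20 patients, and say whether dropout means stopping treatment or having no T2 recording, and in which arm.

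The cost is SAP wording, some extra analysis, and real retention effort to obtain three-night recordings from people who have stopped. No additional participants or scheduled visits are needed. The changes should be settled before outcome data are analysed.

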### **6.1 Statistical analysis**

The Kruskal-Wallis test will be used for intergroup comparisons at each time point (T1 and T2). Intragroup comparisons will be performed by the Friedman test.

Inter-examiner agreement of OMT measurements will be determined by intraclass correlation coefficients (ICCs) and weighted kappa coefficient (Kw'). Effect sizes for statistically significant differences between T1 and T2 will be calculated using the Cohen's d statistic.

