#### Inclusion criteria:

- Patients referred to Ahus or the Fertilitas clinic
- A diagnosis of obstructive sleep apnea according to the current International Classification of Sleep Disorders (ICSD) version 3 criteria {Berry, 2020, The AASM Manual for the Scoring of Sleep and Associated Events: Rules, Terminology and Technical Specifications, Version 2.6., 2014, International classification of sleep disorders, 3rd ed.}, with a respiratory event index (REI) <30.
- Not previously or currently treated with PAP or MAD
- Signed informed, written consent.
- Owning a mobile phone with software compatible for the study application

- Age  $\geq$ 18 year.
- Body mass index  $<$ 30
- Ability to breathe through the nose
- Ability to read and willingness to follow the protocol as described in the written consent form
- Teeth 5-to 5 should be present or fixed by prosthesis or implants.
- No botulinum toxin in facial muscles last three months

Exclusion criteria:

- Failure to fill in at least 70% of days in the electronic sleep diary provided in the mobile app for two weeks.
- Medical or psychiatric conditions which may interfere with the study protocol in the opinion of the investigator. Examples are acute psychosis, drug abuse and dementia. This will be noted in the study inclusion-exclusion document for each approached candidate for the study. The information will then be discussed in an exclusion committee consisting of dr. [name], [name], [name] and [name].
- Tongue-tie as described below. Participants with mouth opening of  $<$ 50% with the tip of the tongue at the incisive papilla compared to total mouth opening will be excluded.

Inclusion criteria will be assessed by the otorhinolaryngologist establishing an OSA diagnosis or the project co-ordinators.

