#### *Wearable technology*

All participants will be asked to wear a Withings Scanwatch,

<https://www.withings.com/be/en/scanwatch>, programmed in research mode.

The research mode setting implies that the watch operates as a sensor. The patients can monitor their own sleep quality data inside the Withing's mobile application. Participants will be instructed to open the Withings application daily.

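### For the diary and wearable endpoints, the only between-arm test is an unadjusted rank test at T1 and at T2, which ignores baseline, the data in between and patients without a T2 value

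*Combined protocol and SAP*

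**What the plan says.** Section 6.1 holds the whole comparative analysis. Between arms: "The Kruskal-Wallis test will be used for intergroup comparisons at each time point (T1 and T2". Within arms: "Intragroup comparisons will be performed by the Friedman test". Cohen's d follows for significant T1-T2 differences. The section gives no baseline adjustment, repeated-measures comparison of the arms or missing-data method. It does not define T1 and T2, and no rule says how diary or watch nights become a T1 or T2 value. Section 6 states intention to treat.

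Two secondary endpoints under Outcomes rest on self-monitoring data: endpoint 4, "Change in objective and subjective sleep quality (PSG and sleep diary, respectively", in its diary part, and endpoint 5, "Change in physiological parameters assessed by wearables". Both are worded as change.

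The monitoring behind them appears to be daily and to run in both arms:
- Section 3.0 describes the control condition as "waiting list with auto-monitoring during the 90-day intervention period".
- The section on the waiting-list condition gives those patients every part of the app except the treatment module. The app contains the diary.
- Under Wearable technology, all participants are asked to wear the watch, and "Participants will be instructed to open the Withings application daily".
- The diary form in the appendix has one column per day.

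The only explicit diary requirement applies before randomisation, as an exclusion criterion: "Failure to fill in at least 70% of days in the electronic sleep diary provided in the mobile app for two weeks". The Outcome evaluation section, which lists what is repeated at 90 days, names neither the diary nor the watch.

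**The concern.** The endpoints are changes measured on a stream of daily data, while the test compares the arms at two isolated points. This has three consequences:
- The T1 test compares randomised groups before treatment and says nothing about effect. The T2 test does not use the baseline value, so stable differences between patients stay in the error term. The Friedman test addresses change only within an arm.
- Nothing recorded between T1 and T2 enters a comparison.
- A patient without a T2 value is not in the T2 comparison, whatever follow-up that patient supplied. This sits badly with the stated intention-to-treat analysis.

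At stake are the precision of these two endpoints and, if leaving is related to how patients fare, their freedom from bias. Because the windows are undefined, they could also be chosen after the data are seen.

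**Working it through.** **1. The plan's own figure.** Section 6.2: two-sided t-test, d = 0.8, 5% level, power 80%. The noncentral t calculation gives 25.52, rounded up to 26 per group, as stated. It concerns AHI and does not bear on this point.

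**2. Share of nights used.** Assume 14 pre-baseline nights (from the two-week diary rule) and 90 follow-up nights, 104 in all.
- One night at each point: 1 - 2/104 = 98% unused.
- Seven nights at each: 1 - 14/104 = 87%.
- Fourteen at each: 1 - 28/104 = 73%.

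**3. Early leavers.** Section 6.2 gives dropout as 25% and also as 20 patients; 25% of 100 is 25. With departures spread evenly over 90 days (assumed):
- 25 leavers: 25 x 45 = 1,125 of 1,125 + 75 x 90 = 7,875 follow-up nights, or 14%.
- 20 leavers: 20 x 45 = 900 of 900 + 80 x 90 = 8,100, or 11%.

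**4. Averaging.** With ρ the between-patient share of one-night variance, an m-night mean has relative variance (1 + (m - 1)ρ)/m. For m = 14 this is 0.35 at ρ = 0.3 and 0.54 at ρ = 0.5. The choice of window therefore matters.

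**5. Baseline adjustment.** Assumptions, none from the documents: one-night SD 1; ρ 0.3-0.5; arm difference growing linearly to 0.4 SD at night 90; SD of patient trends 0.3-0.6; independent night-to-night noise. Nights 77-90 centre on 83.5/90 = 0.928, so the difference in the last 14-night mean is 0.4 x 0.928 = 0.371. For ρ = 0.5 and trend SD 0.3:
- Unadjusted variance: 0.5 + 0.09 x 0.928² + 0.5/14 = 0.5 + 0.0775 + 0.0357 = 0.613.
- Given the 14-night baseline mean, the first term falls to 0.5 x 0.0357/0.5357 = 0.0333, and the total to 0.0333 + 0.0775 + 0.0357 = 0.1465.
- Ratio: 0.1465/0.613 = 0.24. The same formula gives 0.40 (ρ 0.3, trend SD 0.3), 0.61 (0.3, 0.6) and 0.45 (0.5, 0.6).
- Normal-approximation power with 37.5 per arm, from (0.371/√variance) x √(37.5/2) - 1.96: about 54% unadjusted and 99% adjusted, close to the third row of the table.

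**6. Simulated power (%)**, 1,000 runs per row, 50 per arm, 25% leaving at random:

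| ρ | Trend SD | Kruskal-Wallis, one T2 night | Kruskal-Wallis, last 14 nights | Same mean, baseline-adjusted, completers | Slope model, completers | Slope model with leavers |
|---|---|---|---|---|---|---|
| 0.3 | 0.3 | 32.7 | 63.9 | 96.8 | 99.0 | 99.5 |
| 0.3 | 0.6 | 28.3 | 48.5 | 71.9 | 78.1 | 83.3 |
| 0.5 | 0.3 | 35.1 | 50.9 | 98.2 | 99.4 | 99.7 |
| 0.5 | 0.6 | 27.7 | 37.3 | 71.8 | 77.2 | 83.2 |

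Type I error was 3.7-5.9% for all five. Leavers' nights add 0.5, 5.2, 0.3 and 6.0 points. The slope model was given the true variances and the linear shape, so its columns are a best case.

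**7. Why a random intercept alone will not do.** Under the same assumptions, ignoring leavers, compare the true variance of a patient's last-two-week mean with the variance that such a model implies: (patient variance + trend variance/4) + (weekly noise + trend variance/12)/2.
- ρ 0.3, trend SD 0.3: true 0.170; implied (0.0429 + 0.0225) + (0.1 + 0.0075)/2 = 0.119. The standard error is too small by √(0.170/0.119) = 1.20, so a nominal 5% test rejects about 10% of the time.
- ρ 0.5, trend SD 0.6: true 0.379; implied (0.0333 + 0.09) + (0.0714 + 0.03)/2 = 0.174. The factor is 1.48, so about 18%.

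Null simulations with leavers gave about 10-22% with a random intercept only, and about 6-7% with a random slope added.

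**The case against.** The strongest defence is that section 6.1 does not fix the T1 and T2 values. A Kruskal-Wallis test on a 14-night mean fits the text, and this alone recovers part of the loss. Auto-monitoring is also part of what both arms receive, so not every entry need be endpoint data. The endpoints are secondary and unpowered, and a mixed model brings assumptions that a rank test avoids; step 7 shows that a careless one does harm.

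Much of this stands and limits the point. A reader might infer more than the documents support:
- *That recording every night for 90 days is required.* It is a fair inference from the places cited, but no section states it; the only completion rule covers two weeks before baseline.
- *That the plan uses a single night at each time point.* It does not say so. The single-night column in step 6 is not the fair comparator.
- *That every night from early leavers is discarded.* Their pre-baseline diary nights can enter the T1 test, and the plan is silent on missing T2 values; it does not prescribe exclusion.
- *That these are the only sleep outcomes repeated in both arms.* Polysomnography is done on three nights, twice, in both arms.

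One part of the concern survives any choice of window. The stated test does not use the baseline value, leaves the intervening course unanalysed and cannot include a patient who has no T2 value.

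**Conclusion.** The point holds for the diary part of endpoint 4 and for endpoint 5 only. The primary AHI endpoint is untouched, so the change is worth making but not critical.

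Against the most favourable reading of the plan (a 14-night T2 mean), power is 37-64% for Kruskal-Wallis and 72-98% once the same mean is adjusted for baseline. It is tempting to credit the gain to recovered nights from leavers, but these add only about 0-6 points; averaging and baseline adjustment do most of the work.

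These figures rest on assumed variances, linear onset, independent nightly noise, a 14-night baseline and dropout unrelated to outcome. The gains shrink if the effect plateaus or nights are strongly autocorrelated. The baseline gain is also less certain for the watch, because the documents do not say that it is worn before randomisation.

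**What to change.** In section 6.1, for these endpoints:
1. Define the T1 diary value as the mean of the 14 pre-baseline nights. For the watch, use the first recorded week if no earlier data exist. If that week falls after randomisation, say so and leave it out of the outcome weeks. Define the T2 value as the mean of the last 14 nights.
2. Replace Kruskal-Wallis with a mixed model on weekly means from all randomised patients: arm, week, arm x week, baseline, site and sex. Use a random intercept and random slope, or an unstructured or serially correlated covariance.
3. Report the arm difference over the last two weeks with a 95% confidence interval.
4. Add sensitivity analyses for informative dropout and for diary completion that differs by arm. The latter is plausible because only the OMTa arm has video sessions reviewing sleep and adherence during the 90 days.
5. State the expected dropout once, reconciling 25% with 20 patients.

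The cost is SAP wording and a little more analysis work, with no new data. The downside is reliance on missing at random, which item 4 is there to test.
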